3.3 Laboratory and Other Safety Data

3.3.1 Laboratory Test Results

3.3.1.1 Hematology and Serum Chemistry

Analysis Set: Safety Analysis Set

Analysis Hematology

Variable(s): RBC WBC Hemoglobin

WBC Differentials (Neutrophils, Eosinophils, Basophils, Lymphocytes, Monocytes)

Serum Chemistry

(Conjugated

Bilirubin)

Blood Urea Nitrogen Uric Acid Glucose

Calcium Chloride Triglycerides

Total Cholesterol HDL Cholesterol LDL Cholesterol

(Direct Method)

Categories: Results of judgement [Low, Normal, or High relative to the normal reference range]

based on the

reference range

Results based [Meet PCS Criteria, Does not meet PCS Criteria]
on PCS Criteria

Visit: Screening, Placebo Lead-in, Baseline, Week 4, and Week 8

PCS: Baseline (entire pre-dose period), Entire post-dose period

Analytical The following summaries will be provided for the above analysis variable(s)

Method(s):

- (1) Descriptive statistics for observed values at each visit and changes from baseline at each visit (each post-dose visit [Week 4, Week 8] - Baseline)
- (2) Plots over time for each subject
- (3) Shift tables at baseline and each post-dose visit of the results of judgement based on the reference range.
- (4) Frequency distributions of the results based on PCS Criteria during the entire post-dose period

Refer to the Appendix of this Statistical Analysis Plan if a laboratory parameter has lower or upper PCS Criteria.

(5) Shift tables of the results based on PCS Criteria at baseline (entire pre-dose period) and during the entire post-dose period

3.3.1.2 Urinalysis

Analysis Set: Safety Analysis Set

Analysis Protein [-, +-, 1+, 2+, 3+, 4+]

Variable(s):

Glucose [-, 1+, 2+, 3+, 4+, 5+]

Occult blood [-, +-, 1+, 2+, 3+]

Urine pH [Min<= - <=4.9, 5.0<= - <=8.0, 8.1<= - <=Max]

Visit: Screening, Placebo Lead-in, Baseline, Week 4, and Week 8

Analytical The following summaries will be provided for the above analysis variable(s).

Method(s):

(1) Shift tables at baseline and each post-dose visit

3.3.2 Vital Signs, Physical Findings and Other Observations Related to Safety

3.3.2.1 Vital Signs and Weight

Analysis Set: Safety Analysis Set

Analysis Temperature

Variable(s): Systolic Blood Pressure

Diastolic Blood Pressure

Pulse Rate

Weight

Categories: Results based on PCS [Meet PCS Criteria, Does not meet PCS Criteria]
Criteria

Visit: Temperature, Systolic Blood Pressure, Diastolic Blood Pressure, Pulse Rate:
Screening, Placebo Lead-in, Baseline, Week 1, Week 2, Week 4, Week 6, and
Week 8

Weight: Screening, Placebo Lead-in, Baseline, Week 4, and Week 8

PCS: Entire post-dose period

Analytical The following summaries will be provided for the above analysis variable(s).

Method(s):
(1) Descriptive statistics for observed values at each visit and changes from
baseline at each visit (each post-dose visit [Week 1 to Week 8] - Baseline)
(2) Plots over time for each subject
(3) Frequency distributions of the results based on PCS Criteria during the

entire post-dose period
 Refer to the Appendix of this Statistical Analysis Plan if a vital sign parameter has lower or upper PCS Criteria.

3.3.2.2 12-lead ECG

Analysis Set: Safety Analysis Set
 Analysis RR Interval
 Variable(s): PR Interval
 QT Interval
 QRS Interval
 QTcB Interval
 QTcF Interval
 12-Lead ECG Interpretation [Within Normal Limits, Abnormal but not Clinically Significant, Abnormal and Clinically Significant]
 Categories: Results based on PCS [Meet PCS Criteria, Does not meet PCS Criteria]
 Visit: Screening, Placebo Lead-in, Baseline, Week 4, and Week 8
 PCS: Entire post-dose period
 Analytical For each variable other than 12-lead ECG interpretations, summaries (1) to (3) will be provided by treatment group.
 Method(s): For 12-lead ECG interpretation, summary (4) will be provided by treatment group.
 (1) Descriptive statistics for observed values at each visit and changes from baseline at each visit (each post-dose visit [Week 4, Week 8] - Baseline)
 (2) Plots over time for each subject
 (3) Frequency distributions of the results based on PCS Criteria during the entire post-dose period
 Refer to the Appendix of this Statistical Analysis Plan if a ECG laboratory parameter has lower or upper PCS Criteria.
 (4) Shift tables at baseline and each post-dose visit

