	SI	mmol/L	Measured value is \leq 125 or \geq 155
Calcium	CV	mg/dL	Measured value is \leq 0.8-fold of LLN or \geq 1.2-fold of ULN
	SI	mmol/L	Measured value is \leq 0.8-fold of LLN or \geq 1.2-fold of ULN
Triglycerides	CV	mg/dL	Measured value is \geq 1.5-fold of ULN
	SI	mmol/L	Measured value is \geq 1.5-fold of ULN
Total Cholesterol	CV	mg/dL	Measured value is \geq 1.5-fold of ULN
	SI	mmol/L	Measured value is \geq 1.5-fold of ULN
HDL Cholesterol	CV	mg/dL	Measured value is \geq 1.5-fold of ULN
	SI	mmol/L	Measured value is \geq 1.5-fold of ULN
LDL Cholesterol	CV	mg/dL	Measured value is \geq 1.5-fold of ULN
	SI	mmol/L	Measured value is \geq 1.5-fold of ULN

Vital Signs (Blood Pressure, Pulse Rate) and Weight

Analysis Variable(s):	Unit	Definition of PCS
Pulse Rate	bpm	Measured value is ≤ 50 and change* is ≤ -15 or measured value is ≥ 120 and change* is ≥ 15
Diastolic Blood Pressure	mmHg	Measured value is ≤ 50 and change* is ≤ -15 or measured value is ≥ 105 and change* is ≥ 15
Systolic Blood Pressure	mmHg	Measured value is ≤ 90 and change* is ≤ -20 or measured value is ≥ 180 and change* is ≥ 20
Weight	kg	Change rate* is $\leq -7\%$ or $\geq 7\%$

*: Change or change rate from baseline

Resting 12-lead ECG

Analysis Variable(s):	Unit	Definition of PCS
PR Interval	msec	Measured value is < 120 or ≥ 250
QRS Interval	msec	Measured value is < 40 or > 150
QT Interval	msec	Measured value is < 280 or > 500
QTcF Interval	msec	Measured value is < 340 and change* is < -60 or measured value is > 500 and change* is > 60
QTcB Interval	msec	Measured value is < 340 and change* is < -60 or measured value is > 500 and change* is > 60
RR Interval	msec	Measured value is < 500 and change* is ≤ -200 or measured value is > 1200 and change* is ≥ 200

*: Change from baseline

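### The PCS safety tables pool low and high results for 19 parameters, so no planned table counts subjects crossing each PCS limit by direction for vital signs, weight or ECG intervals

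*SAP*

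**What the plan says.** SAP 3.3.2.1 (Vital Signs and Weight) and 3.3.2.2 (12-lead ECG) define one PCS category variable with two levels, "Results based on PCS [Meet PCS Criteria, Does not meet PCS Criteria". SAP 3.3.1.1 (Hematology and Serum Chemistry) uses the same two levels. In all three sections the planned output is "Frequency distributions of the results based on PCS Criteria during the entire post-dose period". Section 3.3.1.1 item (5) adds a shift table of the same variable from the pre-dose to the post-dose period.

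The limits are in SAP Appendix 2. Where a parameter has two limits, they form a single definition joined by 'or'. Systolic pressure is "Measured value is ≤ 90 and change* is ≤ -20 or measured value is ≥ 180 and change* is ≥ 20" and diastolic pressure is "Measured value is ≤ 50 and change* is ≤ -15 or measured value is ≥ 105 and change* is ≥ 15". Weight is defined by percentage change alone, with 7% or more in either direction meeting the criterion.

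The only mention of separate limits in 3.3.2.1 is a pointer: "Refer to the Appendix of this Statistical Analysis Plan if a vital sign parameter has lower or upper PCS Criteria". Sections 3.3.1.1 and 3.3.2.2 carry similar sentences.

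Direction appears in other outputs. Sections 3.3.2.1 and 3.3.2.2 plan descriptive statistics of change from baseline at each visit and plots over time for each subject, and the SAP glossary defines descriptive statistics to include the mean, quartiles, minimum and maximum. Laboratory tests also have shift tables by low, normal or high against the reference range.

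**The concern.** Weight, vital signs and ECGs are named safety endpoints (protocol 5.2.3), and protocol 13.1.5 promises incidences of potentially clinically significant values. The safety questions behind these tables are directional. Protocol 4.1.2 discusses prolongation of QT/QTc, and protocol 4.1.3 lists increased weight among the events seen in more than 5% of subjects in the long-term Japanese study. A count that merges long with short QTcF, or gain with loss, does not say how many subjects had the outcome in question.

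Pooling also affects the comparison between arms. Within an arm the two directions add up. Between arms, an excess in one direction and a deficit in the other work against each other, and the pooled difference can fall to zero. In the laboratory PCS shift table, a subject below the lower limit before dosing and above the upper limit afterwards would appear as meeting the criteria at both times, and so as unchanged.

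**Working it through.** The documents give no PCS rate or count, so there is no planned figure to reproduce. The check has three parts.

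**1. How many parameters are affected (SAP Appendix 2).**
- Laboratory, 9: red cells, white cells, platelets, lymphocytes, uric acid, glucose, potassium, sodium, calcium.
- Vital signs and weight, 4: pulse, diastolic pressure, systolic pressure, weight.
- ECG, 6: PR, QRS, QT, QTcF, QTcB, RR.
- Total: 9 + 4 + 6 = 19.

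Every vital-sign, weight and ECG parameter listed in Appendix 2 (4 + 6 = 10) has two limits.

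**2. Whether the pooled count can mislead.** The group size is 160 (protocol 13.3). The counts below are assumed. The pooled rate is (losses + gains)/160.

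| Placebo loss + gain | Drug loss + gain | Pooled rate | Loss difference (points) | Gain difference (points) |
|---|---|---|---|---|
| 2 + 6 | 6 + 2 | 8/160 = 5.0% in both | +2.5 | −2.5 |
| 4 + 12 | 12 + 4 | 16/160 = 10.0% in both | +5.0 | −5.0 |
| 2 + 14 | 14 + 2 | 16/160 = 10.0% in both | +7.5 | −7.5 |
| 4 + 4 | 12 + 4 | 8/160 = 5.0% vs 16/160 = 10.0% | +5.0 | 0.0 |

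The first three rows cancel exactly. In the fourth, an excess in one direction still raises the pooled rate, but the table does not say which direction it was.

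Partial offset is also possible. With placebo 5 + 5 and drug 1 + 11, the pooled rates are 10/160 = 6.3% and 12/160 = 7.5%, while gain alone is 5/160 = 3.1% and 11/160 = 6.9%.

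**3. Whether a shift of the whole distribution produces this.** Take percentage weight change as normal with mean m and standard deviation s (assumed), and limits at −7 and +7. Then loss = Φ((−7 − m)/s) and gain = 1 − Φ((7 − m)/s).
- m = +1, s = 4: loss = Φ(−2.0) = 2.28%, gain = 1 − Φ(1.5) = 6.68%, pooled 8.96%.
- m = −1, s = 4: loss 6.68%, gain 2.28%, pooled 8.96%.

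For s from 3 to 5 and arm means of ±1 or ±2, the two arms always have the same pooled rate, which ranges from 2.66% to 19.46%.

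The same model shows what the mean-change table would reveal. The standard error of the difference in means is s√(2/160). For s = 4 it is 0.447, so a difference of 2 is 2/0.447 = 4.5 standard errors. The smallest ratio in the range is at s = 5 with means of ±1: 2/0.559 = 3.6.

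**The case against.** The strongest reply is that the PCS table is not the output meant to show whether a parameter rises or falls. That question belongs to the change-from-baseline statistics and subject plots. The shifts that cancel in the pooled count are those that move a mean, and in the model above they amount to at least 3.6 standard errors. This stands. A reader might infer that the plan cannot tell whether the drug raises or lowers weight, blood pressure or ECG intervals, or that a real arm difference would go unseen in the report. The documents do not support either inference.

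A reader might also infer that there are no directional counts at all. That is too broad. SAP 3.1.2 counts adverse events by preferred term, and such terms can carry direction. Those counts depend on investigator judgement and do not apply the PCS limits, so they do not replace the missing rows.

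It can also be said that the pointer sentence recognises lower and upper criteria as distinct. It does, but it leads to definitions joined by 'or' and asks for no separate counts. Following the SAP as written gives the pooled table.

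Finally, protocol 13.1.5 promises incidences without a directional split, so the SAP does not depart from the protocol.

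What remains is narrower. Means do not give the number of subjects beyond a limit. In the assumed 12 + 4 case, 12 of 160 (7.5%) lie beyond one limit, while a quartile cuts off 40 of 160. The quartiles therefore need not move, and the minimum or maximum describes a single subject. Individual plots would have to be counted by hand.

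**Conclusion.** The point holds for the PCS tables. As specified, they pool opposite directions for 19 parameters. For the 10 vital-sign, weight and ECG parameters, no planned table counts subjects beyond the lower or the upper PCS limit by arm. The 9 laboratory parameters are partly covered by the low/normal/high shift tables, though against the reference range and not the PCS limit.

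The possible size is known only by illustration. Under the assumed counts, a pooled difference of 0.0 points can stand for directional differences of 2.5 to 7.5 points. Exact cancellation needs a balanced excess and deficit, and real PCS rates are not in the documents. The effect is confined to descriptive safety tables. No hypothesis test, type I error or sample size is touched. This is a worthwhile low-cost improvement and not a threat to the trial's conclusions.

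**What to change.** In SAP 3.3.1.1 (4), 3.3.2.1 (3) and 3.3.2.2 (3), report two yes/no rows for every parameter with two limits in Appendix 2: 'Meets lower PCS criterion' and 'Meets upper PCS criterion'. Give each row the full safety analysis set as denominator, and count a subject who meets both limits during the post-dose period in each row. A single three-level variable (below, above, neither) would not work, because over the whole post-dose period its levels are not mutually exclusive. In 3.3.1.1 (5), produce one shift table for the lower criterion and one for the upper. The pooled row may be kept alongside.

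The cost is a change to SAP wording and table shells: 19 × 2 = 38 directional rows where there are now 19 pooled ones, and 9 × 2 = 18 laboratory PCS shift tables in place of 9 for the two-limit parameters. No new data are needed, and no threshold or test changes.

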3.3.2.3 Columbia-Suicide Severity Rating Scale (C-SSRS)

Analysis Set: Safety Analysis Set
 Analysis SUICIDAL IDEATION
 Variable(s): Wish to be Dead [Yes, No]

Non-Specific Active Suicidal Thoughts	[Yes, No]
Active Suicidal Ideation with Any Methods (Not Plan) without Intent to Act	[Yes, No]
Active Suicidal Ideation with Some Intent to Act, without Specific Plan	[Yes, No]
Active Suicidal Ideation with Specific Plan and Intent	[Yes, No]
INTENSITY OF IDEATION	
Most Severe Ideation	[Wish to be dead, Non-specific active suicidal thoughts, Active suicidal ideation with any methods (not plan) without intent to act, Active suicidal ideation with some intent to act, without specific plan, Active suicidal ideation with specific plan and intent]
Frequency	[Less than once a week, Once a week, 2-5 times a week, Every day/almost every day, Several times every day]
Duration	[Several seconds to several minutes/For a moment, Less than 1 hour/For a while, 1-4 hours/For a considerable time, 4-8 hours/Almost all hours of the day, More than 8 hours/Persistent or continuous]
Controllability	[Easy to control, A bit difficult but can control, Somewhat difficult but can control, Relatively difficult but can control, Cannot control, No intention to control]

Deterrents	[Desisted to commit suicide due to deterrent(s), Probably desisted to commit suicide due to deterrent(s), Cannot tell if I desisted to commit suicide due to deterrent(s), Probably did not desist to commit suicide due to deterrent(s), Did not desist to commit suicide due to deterrent(s), Not applicable]
Reasons for Suicidal Ideation	[Only to attract someone's attention, revenge, or gain a response, Almost to attract someone's attention, revenge, or gain a response, Fifty-fifty to attract someone's attention, revenge, or gain a response and end pain, Almost to end pain (could not live to put up with the pain and feelings), Only to end pain (could not live while putting up with the pain and feelings), Not applicable]

SUICIDAL BEHAVIOR

Actual Attempt	[Yes, No]
Non-Suicidal Self-Injurious Behavior	[Yes, No]
Interrupted Attempt	[Yes, No]
Aborted Attempt	[Yes, No]
Preparatory Acts or Behavior	[Yes, No]
Suicidal Behavior	[Yes, No]
Completed Suicide (other than screening)	[Yes, No]

Answer for Actual Attempts Only

Most Recent Attempt (Screening Only)	[No physical damage or extremely mild physical damage, Mild physical damage, Moderate physical damage that requires treatment, Slightly severe physical damage that is highly likely to require hospitalization and intensive treatment, Severe physical damage that requires hospitalization and intensive treatment, Death]
Details of no physical damage	[Suicidal behavior that is less likely to bear physical damage, Suicidal behavior that is highly likely to bear physical damage but less likely to die, Suicidal behavior that is highly likely to die even with treatment]
Most Highly Lethal Actual Attempt	[No physical damage or extremely mild physical damage, Mild physical damage, Moderate physical damage that requires treatment, Slightly severe physical damage that is highly likely to require hospitalization and intensive treatment, Severe physical damage that requires hospitalization and intensive treatment, Death]
Details of no physical damage	[Suicidal behavior that is less likely to bear physical damage, Suicidal behavior that is highly likely to bear physical damage but less likely to die, Suicidal behavior that is highly likely to die even with treatment]

First Attempt (Screening Only)	[No physical damage or extremely mild physical damage, Mild physical damage, Moderate physical damage that requires treatment, Slightly severe physical damage that is highly likely to require hospitalization and intensive treatment, Severe physical damage that requires hospitalization and intensive treatment, Death]
Details of no physical damage	[Suicidal behavior that is less likely to bear physical damage, Suicidal behavior that is highly likely to bear physical damage but less likely to die, Suicidal behavior that is highly likely to die even with treatment]
Visit:	Screening, Placebo Lead-in, Baseline, Week 1, Week 2, Week 4, Week 6, and Week 8
Analytical Method(s):	For each variable, summaries (1) will be provided by treatment group. (1) Frequency distributions at each visit

3.3.2.4 Summary of Columbia-Suicide Severity Rating Scale (C-SSRS)

Analysis Set:	Safety Analysis Set
Analysis Variable(s):	Absence of Suicidal Ideation and Suicidal Behavior [Yes, No]
	Non-Suicidal Self-Injurious Behavior [Yes, No]
	Presence of Suicidal Ideation or Suicidal Behavior [Yes, No]
	Suicidal Ideation [Yes, No]
	Wish to be Dead [Yes, No]
	Non-Specific Active Suicidal Thoughts [Yes, No]
	Active Suicidal Ideation with Any Methods (Not Plan) without Intent to Act [Yes, No]
	Active Suicidal Ideation with Some Intent to Act, without Specific Plan [Yes, No]

Active Suicidal Ideation with Specific Plan and Intent	[Yes, No]
Suicidal Behavior	[Yes, No]
Preparatory Acts or Behavior	[Yes, No]
Aborted Attempt	[Yes, No]
Interrupted Attempt	[Yes, No]
Actual Attempt	[Yes, No]
Completed Suicide	[Yes, No]
Visit:	Screening, Baseline (Entire Pre-dose Period), Entire Post-dose Period
Analytical	For each variable, summaries (1) will be provided by treatment group.
Method(s):	(1) Frequency distributions at each visit

4 Significance Level and Confidence Coefficient

- Significance level: 5% (two-sided test)
- Confidence coefficient: 95% (two-sided)

* No statistical testing will be performed if there are less than 5 subjects.

Amendment History (Version Management)

Version	Date	Author	Comments
1	9 June, 2015	PPD	Preparation of Version 1
2	23 May, 2018		Preparation of Version 2

[Appendix 1] Change Comparison Table for Lu AA21004/CCT-004

Page	Before Change	After Change	Reason for Change
Cover	No caption Version 1: Prepared on 9 June, 2015	No caption Version 2: Prepared on 24 May, 2018	
4	Definition of TIME WINDOW -15	Definition of TIME WINDOW -12	Due to error in writing
4	Definition of TIME WINDOW -14 - -5	Definition of TIME WINDOW -11 - -5	Due to error in writing
5	Definition of TIME WINDOW -15	Definition of TIME WINDOW -12	Due to error in writing
5	Definition of TIME WINDOW -14 - -5	Definition of TIME WINDOW -11 - -5	Due to error in writing
6	Definition of TIME WINDOW -15	Definition of TIME WINDOW -12	Due to error in writing
6	Definition of TIME WINDOW -14 - -5	Definition of TIME WINDOW -11 - -5	Due to error in writing
7	Definition of TIME WINDOW -15	Definition of TIME WINDOW -12	Due to error in writing
7	Definition of TIME WINDOW -14 - -5	Definition of TIME WINDOW -11 - -5	Due to error in writing

Page	Before Change	After Change	Reason for Change
7	Others	
 • QT_CF interval = (QT interval) / ([QT_CB interval]² / [QT interval]²)^{0.33} (rounded off to the whole number) • Among the laboratory test items, the following data will not be included if it is from a postprandial specimen. Glucose, lipids (triglycerides, total cholesterol, HDL cholesterol, LDL cholesterol [Direct method]) 	New addition
13	1.2.1 Summary of Demographics and Other Baseline Characteristics Weight (kg) BMI(kg/m ²)	1.2.1 Summary of Demographics and Other Baseline Characteristics Weight (kg) at Baseline BMI (kg/m ²) at Baseline	To make the time point clear
13	1.2.1 Summary of Demographics and Other Baseline Characteristics Pharmacotherapy for Current Episode	1.2.1 Summary of Demographics and Other Baseline Characteristics (Deleted)	Because it was not an item to be collected in the CRF
15	1.2.1 Summary of Demographics and Other Baseline Characteristics Frequency distributions for categorical variables and descriptive statistics for continuous variables will be provided by treatment group and overall.	1.2.1 Summary of Demographics and Other Baseline Characteristics The following summaries will be provided for the above analysis variable(s). When the randomized set is analyzed, the frequency distribution will be provided for each	To make the subjects for distributions clear

Page	Before Change	After Change	Reason for Change
		treatment group and overall. However, weight, BMI, and efficacy endpoints (MADRS total score, HAM-D17 total score, CGI-I score, CGI-S score, SDS total score, DSST score, and PDQ-5 score) will target only the randomized set.	
16	1.2.3 Medication History and Concomitant Medications preferred medication names	1.2.3 Medication History and Concomitant Medications generic names	Due to error in writing

Page	Before Change	After Change	Reason for Change
16	
1.2.3 Medication History and Concomitant Medications
 
(1) Medication History by Preferred Medication Name
 
(2) Concomitant Medications That Started and Stopped Prior to Baseline by Preferred Medication Name
 
(3) Concomitant Medications That Started Prior to and Were Ongoing at Baseline by Preferred Medication Name
 
(4) Concomitant Medications That Started After Baseline by Preferred Medication Name
 
(5) Concomitant Medications That Started Prior to and Were Ongoing at Baseline as well as Those That Started After Baseline by Preferred Medication Name
	
1.2.3 Medication History and Concomitant Medications
 
(1) Frequency distributions for medication history
 
(2) Frequency distributions for concomitant medications
	
Because distributions are no longer necessary

Page	Before Change	After Change	Reason for Change
28	2.3 Other Analysis/Additional Endpoint(s) and Analytical Methods	
2.3 Other Analysis/Additional Endpoint(s) and Analytical Methods
 
(15) The following summaries will be provided if considered appropriate.
 
For the change from baseline in DSST at Week 8 (LOCF) of treatment with double-blind study drug (Week 8 [LOCF] - Baseline), divide the therapeutic effect into direct and indirect effect and estimate each percentage. Here, the effect that affects through the change from baseline in the MADRS total score at Week 8 (LOCF) of treatment with double-blind study drug (Week 8 [LOCF] - Baseline) will be set as an indirect effect and others as a direct effect. Specifically, the following models will be used.
 
Model 1:
 $\text{change DSST} = \text{alpha1} + \text{gamma1} * \text{treatment} + \text{gamma3} * \text{change MADRS} + \text{baseline DSST} + \text{baseline MADRS} + \text{epsilon}$ 
Model 2:
 $\text{change MADRS} = \text{alpha2} + \text{gamma2} * \text{treatment} + \text{baseline DSST} + \text{baseline MADRS} + \text{epsilon}$	New addition

Page	Before Change	After Change	Reason for Change
29	2.4.1 Adjustments for Covariates	2.4.1 Adjustments for Covariates After blind data review, it was decided not to conduct further adjustments for covariates by adding variables.	Because there was no covariate to be added as a result under blind data review
30	2.4.8 Examination of Subgroups Pharmacotherapy for Current Episode	2.4.8 Examination of Subgroups (Deleted)	Because it was not an item to be collected in the CRF
35	3.3.1.1 Hematology and Serum Chemistry [Below the lower limit of PCS Criteria or above the upper limit of PCS Criteria]	3.3.1.1 Hematology and Serum Chemistry [Meet PCS Criteria, Does not meet PCS Criteria]	Because it was corrected to an appropriate expression
35	3.3.1.1 Hematology and Serum Chemistry	3.3.1.1 Hematology and Serum Chemistry PCS: Baseline (entire pre-dose period), Entire post-dose period	Because the visit was clearly stated
35	3.3.1.1 Hematology and Serum Chemistry (4) Number and Percentage of Subjects with Potentially Clinically Significant of Laboratory Parameters	3.3.1.1 Hematology and Serum Chemistry (4) Frequency distributions of the results based on PCS Criteria during the entire post-dose period	Because it was corrected to an appropriate expression
36	3.3.1.1 Hematology and Serum Chemistry	3.3.1.1 Hematology and Serum Chemistry (5) Shift tables of the results based on PCS Criteria at baseline (entire pre-dose period) and during the entire post-dose period	New addition

Page	Before Change	After Change	Reason for Change
36	3.3.1.2 Urinalysis Protein [-, +-, 1+, 2+, 3+, 4+, 5+] Glucose [-, +-, 1+, 2+, 3+, 4+, 5+] Occult blood [-, +-, 1+, 2+, 3+, 4+, 5+]	3.3.1.2 Urinalysis Protein [-, +-, 1+, 2+, 3+, 4+] Glucose [-, 1+, 2+, 3+, 4+, 5+] Occult blood [-, +-, 1+, 2+, 3+]	Because they were corrected to reported values
36	3.3.2.1 Vital Signs and Weight [Below the lower limit of PCS Criteria or above the upper limit of PCS Criteria]	3.3.2.1 Vital Signs and Weight [Meet PCS Criteria, Does not meet PCS Criteria]	Because it was corrected to an appropriate expression
36	3.3.2.1 Vital Signs and Weight	3.3.2.1 Vital Signs and Weight PCS: Entire post-dose period	Because the visit was clearly stated
36	3.3.2.1 Vital Signs and Weight (3) Number and Percentage of Subjects with Potentially Clinically Significant of Vital Signs Parameters	3.3.2.1 Vital Signs and Weight (3) Frequency distributions of the results based on PCS Criteria during the entire post-dose period	Because it was corrected to an appropriate expression
37	3.3.2.2 12-lead ECG	3.3.2.2 12-lead ECG Categories: Results based on PCS Criteria [Meet PCS Criteria, Does not meet PCS Criteria]	New addition
37	3.3.2.2 12-lead ECG	3.3.2.2 12-lead ECG PCS: Entire post-dose period	Because the visit was clearly stated
37	3.3.2.2 12-lead ECG	3.3.2.2 12-lead ECG	Because it was corrected to an appropriate

Page	Before Change	After Change	Reason for Change
	(3) Number and Percentage of Subjects with Potentially Clinically Significant of ECG Parameters	(3) Frequency distributions of the results based on PCS Criteria during the entire post-dose period	expression
41		3.3.2.4 Summary of Columbia-Suicide Severity Rating Scale (C-SSRS)	New addition

[Appendix 2]Definition of PCS Criteria**Hematology and Serum Chemistry**

Analysis	Unit	Unit	Definition of PCS
Variable(s):	system		
Red blood cells	CV	$10^4/\mu\text{L}$	Measured value is ≤ 0.9 -fold of LLN or ≥ 1.1 -fold of ULN
	SI	TI/L	Measured value is ≤ 0.9 -fold of LLN or ≥ 1.1 -fold of ULN
White blood cells	CV	/uL	Measured value is ≤ 2800 or ≥ 16000
	SI	GI/L	Measured value is ≤ 2.8 or ≥ 16
Hemoglobin	CV	g/dL	Measured value is ≤ 0.9 -fold of LLN
	SI	g/L	Measured value is ≤ 0.9 -fold of LLN
Hematocrit	CV	%	Measured value is ≤ 0.9 -fold of LLN
	SI	Fraction of 1	Measured value is ≤ 0.9 -fold of LLN
Platelets	CV	$10^4/\mu\text{L}$	Measured value is ≤ 7.5 or ≥ 70
	SI	GI/L	Measured value is ≤ 75 or ≥ 700
Neutrophils	CV	%	Measured value is ≤ 15
	SI	%	Measured value is ≤ 15
Eosinophils	CV	%	Measured value is ≥ 10
	SI	%	Measured value is ≥ 10
Basophils	CV	%	Measured value is ≥ 5
	SI	%	Measured value is ≥ 5
Lymphocytes	CV	%	Measured value is ≤ 10 or ≥ 80

	SI	%	Measured value is ≤ 10 or ≥ 80
Monocytes	CV	%	Measured value is ≥ 20
	SI	%	Measured value is ≥ 20
Albumin	CV	g/dL	Measured value is ≤ 2.5
	SI	g/L	Measured value is ≤ 25
AST	CV	U/L	Measured value is ≥ 3 -fold of ULN
	SI	U/L	Measured value is ≥ 3 -fold of ULN
ALT	CV	U/L	Measured value is ≥ 3 -fold of ULN
	SI	U/L	Measured value is ≥ 3 -fold of ULN
ALP	CV	U/L	Measured value is ≥ 3 -fold of ULN
	SI	U/L	Measured value is ≥ 3 -fold of ULN
Total Bilirubin	CV	mg/dL	Measured value is ≥ 2
	SI	umol/L	Measured value is ≥ 34.2
Creatinine	CV	mg/dL	Measured value is ≥ 1.5 -fold of ULN
	SI	umol/L	Measured value is ≥ 1.5 -fold of ULN
Creatine Kinase	CV	U/L	Measured value is ≥ 2 -fold of ULN
	SI	U/L	Measured value is ≥ 2 -fold of ULN
Uric Acid	CV	mg/dL	Measured value is ≤ 0.7 -fold of LLN or ≥ 1.3 -fold of ULN

	SI	umol/L	Measured value is \leq 0.7-fold of LLN or \geq 1.3-fold of ULN
Glucose	CV	mg/dL	Measured value is \leq 0.7-fold of LLN or \geq 2.5-fold of ULN
	SI	mmol/L	Measured value is \leq 0.7-fold of LLN or \geq 2.5-fold of ULN
Potassium	CV	mEq/L	Measured value is \leq 3.0 or \geq 5.5
	SI	mmol/L	Measured value is \leq 3.0 or \geq 5.5
Sodium	CV	mEq/L	Measured value is \leq 125 or \geq 155
	SI	mmol/L	Measured value is \leq 125 or \geq 155
Calcium	CV	mg/dL	Measured value is \leq 0.8-fold of LLN or \geq 1.2-fold of ULN
	SI	mmol/L	Measured value is \leq 0.8-fold of LLN or \geq 1.2-fold of ULN
Triglycerides	CV	mg/dL	Measured value is \geq 1.5-fold of ULN
	SI	mmol/L	Measured value is \geq 1.5-fold of ULN
Total Cholesterol	CV	mg/dL	Measured value is \geq 1.5-fold of ULN
	SI	mmol/L	Measured value is \geq 1.5-fold of ULN
HDL Cholesterol	CV	mg/dL	Measured value is \geq 1.5-fold of ULN
	SI	mmol/L	Measured value is \geq 1.5-fold of ULN
LDL Cholesterol	CV	mg/dL	Measured value is \geq 1.5-fold of ULN
	SI	mmol/L	Measured value is \geq 1.5-fold of ULN

Vital Signs (Blood Pressure, Pulse Rate) and Weight

Analysis Variable(s):	Unit	Definition of PCS
Pulse Rate	bpm	Measured value is ≤ 50 and change* is ≤ -15 or measured value is ≥ 120 and change* is ≥ 15
Diastolic Blood Pressure	mmHg	Measured value is ≤ 50 and change* is ≤ -15 or measured value is ≥ 105 and change* is ≥ 15
Systolic Blood Pressure	mmHg	Measured value is ≤ 90 and change* is ≤ -20 or measured value is ≥ 180 and change* is ≥ 20
Weight	kg	Change rate* is $\leq -7\%$ or $\geq 7\%$

*: Change or change rate from baseline

Resting 12-lead ECG

Analysis Variable(s):	Unit	Definition of PCS
PR Interval	msec	Measured value is < 120 or ≥ 250
QRS Interval	msec	Measured value is < 40 or > 150
QT Interval	msec	Measured value is < 280 or > 500
QTcF Interval	msec	Measured value is < 340 and change* is < -60 or measured value is > 500 and change* is > 60
QTcB Interval	msec	Measured value is < 340 and change* is < -60 or measured value is > 500 and change* is > 60
RR Interval	msec	Measured value is < 500 and change* is ≤ -200 or measured value is > 1200 and change* is ≥ 200

*: Change from baseline
